10. HUMAN SUBJECTS

The proposed study will involve participants meeting DSM-IV-TR criteria for Schizophrenia. After completing a screening process, eligible participants will complete weekly study visits during a 7 week time period.

Approximately 71 subjects will be entered into the study at this site. Patients will be recruited from the outpatient services at UCSD Medical Center, a large program with over 2000 active patients and serving a large area in mid-town San Diego. Participants will be 21 years and older and will be in good general health.

Subjects will be selected according to the following inclusion/exclusion criteria:

Inclusion Criteria:

- 1. Adult men or women, 21 years of age or older.
- 2. Meet DSM-IV criteria for Schizophrenia
- 3. Women of childbearing potential must test negative for pregnancy at the time of enrollment based on urine pregnancy test and agree to use a reliable method of birth control during the study.
- 4. Must be on a therapeutic dose of 1 or 2 atypical or typical antipsychotic medications (for example, but not limited to: Clozapine, Olanzapine, Risperidone, Ziprasidone, Aripiprazole, Seroquel) with no major dose changes for at least 4 weeks.
- 5. A minimum PANSS total score of 55 at baseline and a score of at least 4 (moderate) on the subscale of the PANSS (suspiciousness/persecution) at screening.
- 6. Have a Clinical Global Impressions-Severity (CGI-S) scale score of at least 4 (moderately ill) at baseline.
- 7. Must be able to communicate effectively with the investigator and study coordinator and have the ability to provide informed consent.
- 8. Must be able to use nasal spray.
- 9. Must demonstrate an acceptable degree of compliance with medication and procedures in the opinion of the investigator.

Exclusion Criteria:

Subjects will be excluded from the study of they meet any of the following criteria:

- 1. Are pregnant or are breastfeeding
- 2. A urine drug screen performed at screening must not show evidence of recent use of drugs of abuse
- 3. Any active medical condition that in the opinion of the investigator will interfere with the objectives of the study
- 4. Are unsuitable in any way to participate in this study, in the opinion of the investigator.
- 5. Another current DSM-IV diagnosis other than Schizophrenia

Vulnerable populations will not be involved in this study.

Permitted:

Subjects taking up to two sleep medications (diphenhydramine, zolpidem, zaleplon, or diazepam), at a reasonable dose as judged by the investigator, are permitted in this study.

Minor adjustments in sleep medication are acceptable. Patients will be asked to notify the study doctor of any changes to sleep aids.

Discontinuation Criteria

The criteria for enrollment must be followed explicitly. If a subject who does not meet enrollment criteria is inadvertently enrolled, that subject should be discontinued from the study. In addition, subjects will be discontinued from the study and/or from the study in the following circumstances:

- 1. If Exclusion Criteria, as listed above, are observed or develop after entry or enrollment, the subject will be discontinued from the drug/study at the next visit or sooner in the event of a safety exclusion criterion.
- 2. The subject or attending physician requests that the subject be withdrawn from the study.

No subjects will be excluded from participation based on race, ethnicity or gender.

If patients need to be discontinued due to lack of efficacy or intolerance from study medication a study psychiatrist will meet with them an assess their clinical status. Additionally, addressing the patient's ongoing treatment needs (once out of the study) is proactively addressed with the patient on study entry, as in many cases anxiety disorders are chronic conditions in need of ongoing care. Study psychiatrist will discuss non-investigational options for controlling subjects anxiety taking into account treatments subjects has been on in the past, if any. In collaboration with subject, study physician will initiate any treatment of anxiety as deemed appropriate. A referral plan will be developed with subject for him/her to continue treatment with an outpatient psychiatrist. Subject will be followed and cared for by study physician without cost to subject until subject has been able to transfer care to another provider or until patient is deemed stable and has chosen not to pursue care by another provider. After study care of subject will be documented in a medical record.

Sources of Materials

- -Data that will be collected from human subjects for this project includes ratings scales interviews and responses to patient self-rated scales. In addition, blood and urine samples will be collected to perform routine laboratory tests and drug screens.
- -Access to individually identifiable private information about human subjects will be limited to research staff affiliated with the project. Research records will be kept confidential to the extent provided by law. The collection and submission of medical information will be accomplished with strict adherence to professional standards of confidentiality. Patients' medical information will be held in a secure location.
- -Data regarding schizophrenia symptom severity will be collected via interviews with a staff clinician and via patient self-rated scales. Study coordinators will also conduct an interview to establish a medical and psychiatric history for each patient. Blood and urine samples will be collected via the UCSD Medical Center Outpatient Phlebotomy Center. All data will be collected specifically for the proposed research project.

11. RECRUITMENT

Potential subjects will be recruited through several sources. Ads/flyer will be posted in adult clinics, day treatment programs in the county and distributed to colleagues. Approval may be sought from San Diego County Mental Health for recruitment from county run facilities. Recruitment Flyer is included with this application.

12. INFORMED CONSENT

Prior to entry in the trial, the investigator(s) will explain to the potential subjects the aims, methods, reasonably anticipated benefits, and potential hazards of the trial and any discomfort it may entail. Subjects will be informed that they are free to not participate in the trial and that they may withdraw consent to participate at any time. They will be told what alternative treatments are available if they refuse to take part and that such refusal will not prejudice future treatment. Finally, they will be told that competent physicians/lab personnel may examine their records but that personal information will be treated as strictly confidential and will not be publicly available. Subjects will be given the opportunity to ask questions about the study. After this explanation and before entry to the trial, the subject's consent will be obtained. If signed informed consent cannot be obtained, the subjects will not be included in the trial. Subjects who are conservatorized will be able to participate in this study if their conservator signs consent.

13. ALTERNATIVES TO STUDY PARTICIPATION

In order to receive treatment for this disorder it is not necessary to participate in this clinical trial. There is a large variety of FDA approved antipsychotic medications available by prescription from the patient's physician/psychiatrist.

Alternative treatments for schizophrenia include the use of conventional antipsychotic medications, such as, but not limited to, risperidone, olanzapine, quetiapine, or haloperidol. Each of these medications carries their own risk of side effects which can include transient or permanent tardive dyskinesia. Potential benefit of these alternate treatments may include the availability of greater scientific information regarding the medications because these medications are FDA-approved and readily available.

14. POTENTIAL RISKS

All medications have side effects and some of these can be unexpected and unforeseen. Subjects will be closely monitored throughout the trial duration and subjects will be provided emergency contact numbers to ensure 24-hour monitoring.

Nasal Inhalation Oxytocin

The FDA (see appended letter) notes "lack of safety concerns" associated with the clinical use of oxytocin despite ", the length of marketing history of this product in the U.S., the continued availability of the injectable oxytocin in the US and the IN form outside the US" A drug insert provided with IN nasal oxytocin in Europe where it continues to be marketed for lactation lists the following risks; painful uterine contracts; in rare occasions, allergic skin reactions, nausea or headache. Several published studies have used various doses (18- 360 IU) of IN oxytocin administered once to more than a week (e.g. Ansseau et al, 1987; Epperson 1996; Fehm-Wolfsdorf et al, 1988; Westenberg, 1992; Kosfeld et al 2005; Ruis et al, 1981; Heinrichs et al 2003; Fewtrell et al 2005; Bruins et al 1992.) Most studies do not report any adverse effects. One case (Ansseau et al, 87) of a patient developing reversible memory loss, psychosis, and a decrease in plasma sodium and osmolality is reported which is consistent with a picture of SIADH. Some studies reported decreases in verbal recall and memory whereas others did not find this. Other rare mild and transient effects were reported in some studies including, dry mouth, mild dizziness, mild headache, and mild nasal irritation. No effect on blood pressure has been noted.

Risks of Blood Draw

During the study, blood will be drawn 8 times for chemistry basic panel. Some problems from this are: pain, bleeding, bruising, swelling, dizziness, fainting, in rare cases, infection at the insertion site.

Additional Risks

Since this is an experimental treatment there may be some unknown risks that are currently unforeseeable. Subjects will be informed of any significant new findings.

Symptoms of schizophrenia may not improve or may worsen. There is also the possibility that there may be unforeseen risks associated with this test article, which are not yet known.

Allergy Risks

As with any drug, there is a chance that the subjects may have an allergic reaction to the drug. Symptoms of an allergic reaction may be a skin rash, hives or more serious problems like trouble breathing and shock. It is not possible to predict in advance who will develop these problems.

Female subjects will be instructed to use one of the following acceptable methods of birth control throughout the study:

- oral or patch contraception
- Depo-Provera® or other intramuscular injection
- implantation of levonorgestrel (Norplant®) system or an IUD
- barrier methods (combination of diaphragm and spermicide or condom and spermicide)

Risk of Disclosure

Subjects will be asked to provide a urine sample to be tested for certain types of controlled substances that may be regulated by law. Additionally, information about subjects' mental and physical health collected

throughout the study will also be kept with research records. Disclosure of this kind of information is a risk of being in the study. Disclosure of this kind can affect a subjects' ability to get a job, obtain life or health insurance, employment or ability to adopt children. Confidentiality risk will be managed by keeping subjects' information completely confidential, stored in a secured location and disclosed only as required by law.

Other Risks

Participation includes a urine toxicology and pregnancy test. It is possible that a positive drug screen may becomeknown outside of the research setting and it could potentially jeopardize the subjects' ability to acquire a job or insurance.

EEG mu suppression paradigm exposes subjects to the application of electrodes. The possibility of skin irritation from application of paste exists, however, is unlikely given that the salt concentration of the paste is similar to that of human sweat.

As with any drug, participants are faced with the possibility of side effects. Other studies of oxytocin report side effects such as dry mouth, mild dizziness, mild headache, and mild nasal irritation. Because the treatment proposed in the study is investigational, there is a risk that participants' symptoms of schizophrenia may stay the same or worsen. There may also be other risks or side effects which are currently unknown. Possible side effects from venipuncture include faintness, inflammation of the vein, pain, bruising, or bleeding at the site of puncture. There is also a slight possibility of infection as a result of the blood draw procedure. Women of childbearing potential are asked to utilize an approved method of birth control during study participation as risks to a fetus are unknown. Urine and blood samples collected during this study will be utilized to screen for illicit chemical substances. The results of these tests will be kept confidential and may be disclosed as required by law. It is possible that positive drug screen results may become known outside of the research setting; if this information were disclosed, it could potentially jeopardize a subject's ability to obtain employment or insurance. Additionally, some of the information to be collected for this study includes information on patient diagnosis. There is a risk that this information can become known outside of the research setting. This information, if disclosed, could also potentially jeopardize a patient's ability to obtain employment or insurance. The study staff will manage this risk by storing all study information in a secure location in a locked facility. No information about subject participation will be provided to anyone outside of the necessary research staff without subject's written permission.

Potential subjects will be recruited through several sources in the community surrounding the UCSD Medical Center. Flyers will be posted in adult clinics, day treatment programs, and distributed to colleagues. Advertisements will be placed in local community publications and online forums, and a local press release will be made.

Prior to entry in the trial, the investigator(s) or study coordinator(s) will explain to the potential subjects the aims, methods, reasonably anticipated benefits, and potential hazards of the trial and any discomfort it may entail. Subjects will be informed that they are free to not participate in the trial and that they may withdraw consent to participate at any time. They will be told what alternative treatments are available if they refuse to take part and that such refusal will not prejudice future treatment. Finally, they will be told that competent physicians/lab personnel may examine their records but that personal information will be treated as strictly confidential and will not be publicly available. Subjects will be given the opportunity to ask questions about the study. After this explanation and before entry to the trial, the subject's consent will be obtained and documented via signature of an informed consent form by both the patient and the person conducting the informed consent discussion. If signed informed consent cannot be obtained, the subjects will not be included in the trial. Subjects who are conservatorized will be able to participate in this study if their conservator signs a consent form on their behalf.

15. RISK MANAGEMENT PROCEDURES AND ADEQUACY OF RESOURCES

A staff that is highly qualified in the assessment and treatment of schizophrenia in adults will closely monitor subjects in this study. This monitoring includes the frequent periodic assessments involved in the study protocol, which occur at intervals of 1 week long. Study drug will be administered on site following both baseline visits. Mid-week calls are set up following both baseline visits along with a study treatment follow up visit. In addition, subjects will be monitored throughout the study for any adverse events. Subjects will be instructed by the Investigator to report the occurrence of any adverse events immediately. At the beginning of each treatment period, the Investigator will query the subjects, in a generalized fashion, whether any clinical adverse events have occurred since the last visit. Any serious or unexpected event, including death due to any cause, whether or not related to the study drug or procedures, will be reported to the UCSD HRPP within 10 days.

After a thorough literature search was performed and confirmed the relative safety profile of this drug, the following additional safety measures were added in an attempt to be thorough.

Biological safety measures include blood chemistry and urine osmolality to monitor for SIADH. These tests will be done at screening and at every visit after randomization. In addition a blood metabolic assay (glucose, liver enzymes) will be conducted at each visit.

If any clinical worsening or serious adverse event is detected during the course of the trial that cannot be managed by a dose adjustment, the subjects will be discontinued from the protocol.

It is my intention to provide contact information for study staff to the subjects and reiterate this information at the time of each visit. Contact information for PI, and Drs. [name] and [name], are listed on the diary form that will be provided to the subject at each visit. Study subjects will be encouraged, as documented in the consent and on the separate diary form, to contact the study team with medical concerns, reactions, and experiences. Subjects will be given a diary form to complete upon each use for administrations that are done between site visits. This diary form includes 24 hour emergency contact information (including PI, sub-Is and study staff), nearest emergency department from subject's residence and concomitant medication diary.

At the termination of the project or in the event that any subjects will need to be discontinued from the study due to lack of efficacy or an adverse event, one of the study doctors will arrange for subjects to receive appropriate treatment for any symptoms that require stabilization. The study staff will also help arrange routine follow-up for subjects' symptoms of schizophrenia (e.g., referral if required) and will provide standard medication treatment of schizophrenia to subjects until such follow up is available.

Subjects will have 24-hour access to emergency psychiatric care and will be provided with a means of contacting the on-call study doctors and research staff at the UCSD Medical Center. Subjects will be informed and encouraged to contact study physicians and staff immediately with medical concerns or unusual reactions. This information will also be listed on the diary cards provided to subjects at every visit along with the identification of the closest Emergency Department location to their residence. PI and sub-investigator phone numbers for 24-hour access has been listed in the consent form.

Confidentiality risk will be managed by keeping all of each subjects' data completely confidential, and stored in a secured filing cabinet and on Clinical Conductor, a secure, password protected clinical trials administration database. The data collected for this investigation will be used for research and treatment purposes only. Data will be available only to those directly involved with the study, HRPP, and the FDA.

Research records will be kept confidential to the extent allowed by law. The following people will have access to the study data collected for this study: [name] and study staff listed below, UCSD HRPP, the grant funding agency, National Institute of Mental Health, representatives of the grant funding agency and government agencies where permitted or required by law (such as the Food and Drug Administration (FDA) and the United States Department of Health and Human Services).

Research records will be kept confidential to the extent provided by law. The National Institute of Mental Health, including its agents and contractors, the United States Food and Drug Administration or other regulatory authorities, and similar ethics committees and regulatory agencies in other countries, as well as the UCSD Institutional Review Board,mayreview original medical and research records in connection with this study. Medical records that contain subject identity will be treated as confidential and will be shared only with these agencies, or as required by law. Medical information may be held and processed on a computer. The results of this research may be published in scientific journals or presented at medical meetings, however subject name will not appear in any publications or reports produced from this study.

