4. ESTIMATED DURATION OF THE STUDY

Study enrollment will occur over approximately a two year period. Completion of the entire protocol, including subject recruitment, study procedure execution, and statistical analysis is anticipated to take no longer than four years.

Each subject will be enrolled for a 7 week period, including a screening phase. Study procedures involve weekly clinic visits as an outpatient. Approximately 72 patients will be randomly assigned to either 84 IU of oxytocin (equivalent to 42 IU BID), 168 IU of oxytocin (84 IU BID) or vehicle placebo. The doses of oxytocin are based upon previous studies in humans showing improvement in schizophrenia related changes in behavior and brain function (Kosfeld et al, 2005; Kirsch 2005; Heinrich M 2003).

The total study duration for each individual subject will be approximately 7 weeks, which includes a 7-day screening period, a baseline (randomization) visit, and the six-week treatment phase.

Participants will remain on their current antipsychotic medication and dose throughout the study.

5. LAY LANGUAGE SUMMARY OR SYNOPSIS (no more than one paragraph)

The purpose of this study is to test whether or not people with schizophrenia feel improvement in their symptoms when oxytocin nasal spray is added to their current medications. Volunteers will be randomly assigned to one of three groups; a higher dose group, a lower dose group, or a group who receives a nasal spray with no medication in it (placebo). Volunteers will be asked questions about their mental and physical health as well as take several computer tests to track any changes over the 7 weeks of the study.

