- Complete a questionnaire about symptoms of paranoia and sexual functioning
- Complete a test onability to recognize emotions called the Penn Emotion Recognition Test (ER-40).

Additionally at Visit 8 (week 6 or Early Termination);

- Complete a series of activities which will be used to measure process of thought called the CMINDS® and MSCEIT™ ME
- Have an additional blood sample taken (about 1 tablespoon) to monitor study drug levels in the blood
- EEG paradigm will be conducted

Follow Up Call

The volunteer will be asked to contact the study site one week after the last study drug dose to report taking any new medications or any unusual experiences since stopping the study drug.

Administration and dispensing of the study medication:

Except the one time challenge dose, this is a double-blind study, participants will be randomized to receive one of three possible intranasal study medications adjunctive to their antipsychotics: oxytocin 84 IU, oxytocin 168 IU or placebo (vehicle without oxytocin). Randomization will be performed stratifying gender groups, type of antipsychotic (typical versus atypical) and severity of symptoms based upon PANSS score (<90 versus >90) so that gender, symptom severity and antipsychotic type are distributed relatively evenly across treatment groups. Bottles containing placebo or two different concentrations of oxytocin will be formulated (See Study Drug Formulation below) so that the concentration of oxytocin in the high dose (168 IU) will be double that of the low dose (84 IU). All subjects will be instructed to spray 7 pumps of the spray bottle (one in each nostril, alternating nostrils) to achieve correct dose in the morning and again in the afternoon. Subjects will be given enough study drug at the time of the visit to last until the next visit with extra to cover approximately three additional days. Each pump bottle has 5 ml (300 IU) which is enough for 2.5 days of study drug. Therefore, subjects will be given one spray bottle supply at the time of each visit. The weight of each bottle will be recorded prior to dispensing. After all procedures are performed on baseline visit and study drug is randomly assigned, a dose of the study drug will be taken at the study site, in the presence of a staff member to insure correct administration.

Study Drug Compliance

- 1. Subjects will be instructed on proper use of the nasal device from study staff.

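### The only post-treatment safety contact is a call left to the subject, with no schedule entry and no staff fallback; nearby safety text does not fit the one-baseline, one-period design

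*Combined protocol and SAP*

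**What the plan says.** **Design.** Section 4 describes each subject's participation as "a 7-day screening period, a baseline (randomization) visit, and the six-week treatment phase", about 7 weeks in all. The schedule table in section 9 agrees: one Baseline, one mid-week call, then Visits 3 to 8, the last on Day 42.

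**After the last dose.** The Follow Up Call paragraph in section 9 says: "The volunteer will be asked to contact the study site one week after the last study drug dose". The purpose is to report new medications or unusual experiences. The paragraph does not say what staff do if no call comes.

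**Risk management (section 15).** This section speaks of more than one baseline and more than one period:
- On supervised dosing, it says: "Study drug will be administered on site following both baseline visits".
- On adverse events, it says: "At the beginning of each treatment period, the Investigator will query the subjects, in a generalized fashion, whether any clinical adverse events have occurred" (the sentence goes on to make the question reach back to the preceding visit).
- On calls and follow-up, it says: "Mid-week calls are set up following both baseline visits along with a study treatment follow up visit".

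The same paragraph also gives a general assurance that "subjects will be monitored throughout the study for any adverse events".

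**Care after discontinuation.** The Discontinuation Criteria in section 10 say: "Study psychiatrist will discuss non-investigational options for controlling subjects anxiety". Section 15 says that study staff "will provide standard medication treatment of schizophrenia to subjects until such follow up is available". Exclusion criterion 5 in section 10 rules out any current DSM-IV diagnosis besides schizophrenia.

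**The concern.** Specific Aim 5 asks whether daily intranasal oxytocin is safe, feasible and acceptable enough to develop further. That calls for adverse events to be sought in the same way from every subject over the whole period in which they count. Under Safety Endpoints in section 9, an event is treatment-emergent if it starts or worsens after the first dose, and no closing date is given. Events in the week after the last dose therefore belong in the tables. The one contact designed to capture them is passive, so a missing call is ambiguous. If the subjects who phone differ from those who do not, for instance because an event prompts the call, the post-treatment counts in each arm depend on calling behaviour as well as on the drug.

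The misfitting text in sections 10 and 15 is a lesser matter. Site staff reading section 15 alone meet visits and periods that this trial does not have, and staff reading section 10 meet care instructions written around a different disorder.

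**Working it through.** No arithmetic beyond counting applies, and the plan states no figure to reproduce. The check sets the texts side by side.

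| Item | Sections 4 and 9 | Section 15 |
|---|---|---|
| Baseline visits | 1 | both, i.e. 2 |
| Treatment periods | 1, of six weeks | each, i.e. more than one |
| Mid-week calls | 1, on day 3 or 4 | after both baselines |
| Contact after the last dose | subject's call, in the procedures text only | a follow-up visit, timing not stated |

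**1. Is the post-treatment call in the schedule?** No. The last column is Visit 8 or early termination, Day 42. If the last dose falls on about Day 42, the call is due on about 42 + 7 = Day 49. The duration in section 4 is used up by 1 week of screening plus 6 weeks of treatment = 7 weeks, so the call also lies outside the stated duration, which is given as approximate.

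**2. Is there a fallback?** Not for this call. For the mid-week call, the visit descriptions in section 9 provide that staff will try to reach the volunteer as an alternative to the volunteer phoning in. The mid-week call also has its own schedule column, with Concomitant Meds and Adverse Events marked. The follow-up call has neither.

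**3. Do the events matter for the analysis?** Yes. The treatment-emergent definition has a start and no end, so an event in the week after the last dose qualifies.

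**4. How often are adverse events asked about on treatment?** The Adverse Events row is marked at Baseline (1), the mid-week call (1) and Visits 3 to 8 (6): 1 + 1 + 6 = 8 contacts. The text for Visits 3 to 8 also has subjects questioned about events each time. On-treatment querying is therefore defined, whatever section 15 says about periods.

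**5. Does the care text agree with itself?** Section 10 justifies its plan by the chronic nature of anxiety disorders and directs attention to anxiety. Section 15 refers to stabilising symptoms and treating schizophrenia. With exclusion 5 in force, the section 10 wording does not describe the enrolled population.

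**6. Where might the misfitting text come from?** Section 6 says that the preceding study was a crossover, and the safety analysis in section 9 still lists sequence and period as ANOVA factors. Carry-over from a crossover protocol is a reasonable inference for the section 15 wording, but it remains an inference.

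**The case against.** The case on the other side is strong on several points, and most of it stands.

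- **Frequency of questioning.** A reader might infer from section 15 that the investigator asks about adverse events only once, at the start of the single period. The documents do not support that. The sentence itself reaches back to the preceding visit, its paragraph promises monitoring throughout, and the schedule and visit text set out the eight contacts. What remains is wording that does not fit the design.
- **The follow-up visit.** A reader might also infer that section 15 requires a visit after the last dose, in conflict with the call. Section 15 never places that visit after the last dose; it could be an on-treatment visit. Its timing is unclear, and that is all that can be said.
- **Care after discontinuation.** It is tempting to say that this contradicts the schedule. The schedule is silent on such care, and both care texts could be followed together. The mismatch is with the other care text and with the study population.
- **Other routes for reporting.** Subjects are told to report events at once and have 24-hour contact with study doctors, so post-treatment events are not wholly invisible. This stands, but these routes are also passive and do not separate silence from absence of events.
- **Staff fallback.** Adding one is an improvement to ascertainment; it does not resolve a contradiction. This stands too. It is nevertheless the practice the protocol already adopts for its other call.

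**Conclusion.** The concern holds in a limited form. The protocol's only defined post-treatment safety contact is unscheduled and passive, while the treatment-emergent definition leaves that time open. Post-treatment events can therefore go unrecorded in a way that the data cannot reveal. The number of subjects affected cannot be stated, because the documents give no call-in rate; any count would be an assumption. This conclusion takes the treatment-emergent definition as written and assumes that no staff-initiated contact is described elsewhere in the plan.

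The section 15 wording on baselines and periods, and the section 10 wording on anxiety, are drafting inconsistencies that should be cleared up. They do not show that on-treatment adverse events would be missed. No sample size, alpha, power or efficacy result depends on any of this. It is a cheap improvement to safety ascertainment, worth making but not one on which the trial stands or falls.

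**What to change.** 1. Add a column to the section 9 schedule for the contact one week after the last dose, with Adverse Events and Concomitant Meds marked, and let the duration in section 4 reflect it.
2. State in the Follow Up Call paragraph that existing staff will try to reach any subject who does not phone, as the protocol already provides for the mid-week call. Record whether contact was made, so that no event and no contact are distinguishable.
3. Reconcile section 15 with sections 4 and 9 on the number of baselines, treatment periods and mid-week calls, and state when its follow-up visit takes place or whether it is the same contact as the call.
4. Reconcile the discontinuation text in section 10 with section 15 and with exclusion criterion 5. Which care applies is for the clinical investigators to settle; no rule is proposed here.

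The cost is text edits and at most one staff phone call per subject.
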